Study To Evaluate The Efficacy Of Tofacitinib In Patients With SJS/TEN

ClinicalTrials.gov ID NCT06474078

Sponsor Chang Gung Memorial Hospital

Information provided by [name], Chang Gung Memorial Hospital (Responsible Party)

Study Overview

Brief Summary

The goal of this study is to evaluate the effect of tofacitinib in patients with Stevens-Johnson Syndrome (SJS) and Toxic Epidermal Necrolysis (TEN). The primary outcome of the study is the time to complete re-epithelialization. The secondary outcomes are to determine mortality, length of hospitalization, adverse events, the time to beginning of epithelialization, the time to halting of progression of SJS/TEN, ocular complications, and infections.

Detailed Description

Stevens-Johnson syndrome (SJS) and toxic epidermal necrolysis (TEN) belong to life-threatening severe cutaneous adverse drug reactions. SJS/TEN is classified by the extent of the detachment over the total body-surface area: SJS (<10%), SJS-TEN overlap (10%-30%), and TEN (>30%). TEN has the highest mortality (30-35%); SJS and transitional forms correspond to the same syndrome, but with less extensive skin detachment and a lower mortality (5-15%). Currently, there is still no conclusive effective immunomodulator treatment for SJS/TEN. And, there is still a clinical unmet need for the treatment of SJS/TEN.

According to our past research reports, interleukin-15 (IL-15) plays an important role in SJS/TEN, which is related to disease severity and mortality. Janus kinase (JAK) inhibitors can inhibit the downstream JAK to inhibit the production and transmission of inflammatory cytokines, as a treatment for severe skin drug hypersensitivity reactions. Tofacitinib, a JAK1/3 inhibitor, is an intervention known to effectively treat several inflammatory diseases including rheumatoid arthritis, psoriatic arthritis, and ulcerative colitis. Notably, a recent study identified a potential therapeutic target with JAK-STAT pathway in a patient with recalcitrant and refractory drug rash with eosinophilia and systemic symptoms (DRESS). Based the current evidence, a targeting therapy to IL-15 by tofacitinib treatment are suggesting likely to be effective in treating SJS/TEN.

This is an "open label" study, all patients enrolled in the study will receive the active medication; meaning that there will not be a placebo or control group. The aims of this project are (1) to investigate the effect of tofacitinib treatment for SJS/TEN patients, including healing time, mortality rate, adverse events, beginning of re-epithelialization time, internal organ recovery time, and ocular complications, and (2) to investigate the molecular mechanism of SJS/TEN after tofacitinib treatment through collection of timed samples to include DNA, RNA, PBMCs, blister cells and supernatant and skin tissue.

The primary outcome of the study is the time to complete re-epithelialization as defined by complete absence of erosion on the skin. The secondary outcomes are to determine the time to beginning of epithelialization (defined as the time to start re-epithelialization of the erosions on the skin and mucosa), the time to halting of progression of SJS/TEN (considered significant progression if there are any new blistering lesions or any new detached or detachable skin), mortality, length of hospitalization, ocular complications, infections, and adverse events. The investigators also determine the molecular and cellular mechanisms of SJS/TEN through collection of timed samples to include DNA, RNA, PBMCs, blister cells and supernatant and skin tissue.

Official Title

An Open-Label Pilot Study to Evaluate the Safety, Tolerability, and Efficacy of Tofacitinib in Patients With Stevens-Johnson Syndrome (SJS) and Toxic Epidermal Necrolysis (TEN)

Intervention / Treatment

Drug: Tofacitinib

Other Study ID Numbers

IRB No. 202102411A3

Contacts and Locations

This section provides the contact details for those conducting the study, and information on where this study is being conducted.

Study Contact (Project Leader)

Name: [name]

[contact] [name]

Email: [contact]

Study Contact Backup (Co-Investigator)

Name: [name]
[contact] [name]
Email: [contact]

Name: [name]
[contact] [name]
Email: [contact]

Participation Criteria

Researchers look for people who fit a certain description, called eligibility criteria. Some examples of these criteria are a person's general health condition or prior treatments.

Eligibility Criteria

Description

Inclusion Criteria:

1. Willing to sign informed consent form
2. Subject has been diagnosed with Stevens-Johnson syndrome or toxic epidermal necrolysis by at least two dermatologists.
3. Male or female aged over 20 years old and under 90 years old.

Exclusion Criteria:

1. Subject or legally authorized representative is not willing to provide informed consent.
2. Women who are pregnant or breastfeeding
3. Subject has an active, untreated, or serious infectious disease that is ineffective in treatment, such as sepsis.
4. Subject suffers from severe life-threatening cardiac arrhythmia, such as ventricular tachycardia, have had myocardial infarction (myocardial infarction), severe hypertension that has not responded to treatment within the past week, or other cardiologist diagnosed severe cardiovascular disease
5. Subject has active viral hepatitis
6. Subject has active tuberculosis
7. Subject received live vaccination during the illness

Study Protocol

This section provides details of the study plan, including how the study is designed and what the study is measuring.

How is the study designed?

Design Details

Primary Purpose : Treatment

Allocation : N/A

Interventional Model : Single Group Assignment

Masking : None (Open Label)

Arms and Interventions

Participant Group/Arm 	Intervention/Treatment 

Experimental: Tofacitinib treatment
 
1. Meet the conditions of inclusion and exclusion, seek the consent of the patient2. Fill out the case report form3. Blood test and physiological assessment, and do serum granulysin concentration and peripheral blood mononuclear spherical granulysin expression analysis4. Tofacitinib administration: The experimental group received tofacitinib 5mg-10mg, twice daily, for the first week; and maintained tofacitinib 5mg-10mg, daily, for the second week.	
Drug: Tofacitinib
 
• Dosage/Frequency: 5mg - 10mg, oral, twice daily• Other Names:
▫ XELJANZ

What is the study measuring?

Primary Outcome Measures

Outcome Measure	Measure Description	Time Frame
Time to complete re-epithelialization of SJS/TEN	Definition of complete re-epithelialization as the absence of erosions on the skin.	up to 4 weeks

Secondary Outcome Measures

Outcome Measure	Measure Description	Time Frame
Mortality	Number of participants with mortality at 30 days, 3 months and 1 year	up to 1 year
Length of hospitalization	Duration of hospital stay	up to 3 months
Adverse events	Adverse events related to the treatment with tofacitinib	up to 3 months

Study endpoint

The endpoint of this clinical trial was defined as the absence of serious or treatment-related adverse events within three weeks after the final tofacitinib dose. Most SJS/TEN patients were monitored for 3–4 weeks post-treatment, with the total observation period spanning 1–2 months. Patients without AEs during this window were considered to have completed the trial and met the safety endpoint.

Study duration

Start Date from 2022-08-01 to 2025-07-31

Statistical Analysis Plan

For evaluating the time taken to heal skin erosion, the Kaplan-Meier product-limit estimates method was performed.

Collaborators and Investigators

This is where you will find people and organizations involved with this study.

Sponsor

Chang Gung Memorial Hospital

Investigators

- Principal Investigator: [name], Chang Gung Memorial Hospital

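### Mortality is to be counted at 3 months and 1 year, but the stated observation period ends at 1–2 months and no later check of vital status is described

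*Combined protocol and SAP*

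**What the plan says.** Four parts of the document bear on how long patients are followed.

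- **Secondary Outcome Measures.** Mortality is defined as "Number of participants with mortality at 30 days, 3 months and 1 year", with a time frame of up to 1 year. Adverse events and length of hospitalization each run up to 3 months.
- **Study endpoint.** The endpoint is the "absence of serious or treatment-related adverse events within three weeks after the final tofacitinib dose". The section continues: "Most SJS/TEN patients were monitored for 3–4 weeks post-treatment", "with the total observation period spanning 1–2 months". It closes with: "Patients without AEs during this window were considered to have completed the trial and met the safety endpoint".
- **Arms and Interventions.** Dosing lasts two weeks: "twice daily, for the first week; and maintained tofacitinib 5mg-10mg, daily, for the second week".
- **Statistical Analysis Plan.** The plan is one sentence: "For evaluating the time taken to heal skin erosion, the Kaplan-Meier product-limit estimates method was performed".

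The Detailed Description names mortality among the aims ("including healing time, mortality rate, adverse events"). Study duration gives one pair of dates, 2022-08-01 to 2025-07-31, without saying whether the second closes enrolment or follow-up. No visit, call, record check or other means of learning vital status at month 3 or month 12 is described.

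**The concern.** Observation that ends at 1–2 months cannot by itself supply a death count at 3 months or 1 year. This is more than a missing schedule, because two statements in the document give different lengths of follow-up. The analysis plan does not resolve them: it covers skin healing only and does not say how a patient of unknown status enters the mortality count.

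The measure is a raw number of deaths. If nobody looks after the window closes, a patient who dies in month 5 is counted in the same way as a survivor. A reader of the results could not tell a complete 1-year count from an incomplete one. The trial has no control group and the disease is described as life-threatening, so an incomplete count could pass for favourable survival. No stated test or decision depends on these counts. What is at stake is what the pilot can report about mortality.

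**Working it through.** **Inputs.** Dosing of 14 days (Arms and Interventions); monitoring of 3–4 weeks after treatment and 1–2 months in total (Study endpoint); mortality at 3 months and 1 year (Secondary Outcome Measures). Conversions: 1 month = 30 days, 2 months = 61, 3 months = 91, 1 year = 365.

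**Step 1: reproduce the plan's own figure.** 14 + 21 = 35 days and 14 + 28 = 42 days. Both lie within 30–61 days, so the stated 1–2 months agrees with its components.

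**Step 2: compare with the mortality horizons.** Share covered = observation ÷ horizon; days left = horizon − observation.

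| Observation (days) | Share of 91 | Days left to 91 | Share of 365 | Days left to 365 |
|---|---|---|---|---|
| 30 | 33.0% | 61 | 8.2% | 335 |
| 35 | 38.5% | 56 | 9.6% | 330 |
| 42 | 46.2% | 49 | 11.5% | 323 |
| 61 | 67.0% | 30 | 16.7% | 304 |

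Day 30 falls inside the window for a patient who takes the full course and is then monitored for three weeks (35 days). The difficulty lies at the two later points.

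**Step 3: direction and size of the error.** Let D be deaths within the window and L later deaths up to the horizon. The true count is D + L. A count limited to the window is D, so the error is −L, which is never positive. The relative shortfall is L ÷ (D + L). The documents give neither a sample size nor the timing of deaths, so L is unknown. As an assumed range only, suppose 10% die in the window and a further 0%, 2%, 5% or 10% die later within the year:

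- 0 ÷ 10 = 0%
- 2 ÷ 12 = 17%
- 5 ÷ 15 = 33%
- 10 ÷ 20 = 50%

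**Step 4: study dates.** From 2022-08-01 to 2025-07-31 is 1,096 days, counting both ends. If 2025-07-31 ends follow-up, anyone enrolled after 2024-07-31 cannot reach 1 year. That is the last 365 ÷ 1,096 = 33% of the calendar period.

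**Step 5: would Kaplan-Meier repair it?** Only with active follow-up. Assume 20 patients, 19 censored at day 42, and one death learned by chance at day 200. One patient is then at risk, so estimated survival falls to 1 − 1/1 = 0 and estimated mortality is 100%. If the other 19 are in fact alive, the true figure is 1/20 = 5%. The example is extreme by design. It shows what happens when late deaths arrive passively while survivors are censored early, and it is no argument against Kaplan-Meier when status is actively sought.

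**The case against.** The strongest reply is that the 1–2 month sentence describes a safety window only. It stands under an endpoint defined by adverse events, it concludes that the safety endpoint is met, and it speaks of most patients, not all. Mortality has its own time frame of up to 1 year, and a specific outcome time frame can reasonably prevail over a general description. This reading is plausible, and it rules out saying that late deaths will be missed.

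It does not settle the matter, for three reasons. The observation period is called total, and completion refers to the trial, neither with any qualification. Even as a safety window, 1–2 months is shorter than the 3-month time frame for adverse events; up to 3 months might be only a ceiling there, but mortality is tied to named time points. And if year-long follow-up was intended, the document still does not say how status is learned or how an unknown is counted.

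Three stronger inferences are tempting and are not supported:

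- **That mortality will be understated.** This depends on which section governs and on whether any death falls after the window. Neither is known.
- **That the uncovered share of days is the share of deaths missed.** The document gives no timing of deaths, so the table measures calendar time and nothing more.
- **That follow-up ends at 1–2 months for everyone.** The completion rule covers only patients without adverse events. For the others no end of follow-up is stated.

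**Conclusion.** The point holds in conditional form. The outcome table and the Study endpoint section give different lengths of follow-up and must be reconciled. If the latter governs, observation covers 33–67% of the time to 3 months and 8–17% of the time to 1 year. The two later death counts are then incompletely ascertained and can err only downward. How many deaths would be missed cannot be computed and may be none.

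The coverage figures assume that the stated 1–2 months applies and is counted from about the start of treatment; the document gives no time origin. The percentages in Step 3 and the 20-patient example rest on assumed values and are not estimates for this trial. Mortality is a secondary outcome of a single-arm pilot, so this is something the sponsor should correct. It does not affect the primary healing analysis.

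**What to change.** 1. Reconcile the Study endpoint section with every time frame in the outcome tables, including the 3 months for adverse events. State that completing the 1–2 month window does not end mortality follow-up. Labelling the window as being for adverse events and healing only would not do, since it would conflict with the 3-month time frame for adverse events.
2. Ascertain vital status for every treated patient, with or without adverse events, at day 30, month 3 and month 12 from first dose, by hospital record or telephone.
3. State whether 2025-07-31 ends enrolment or follow-up. If it ends follow-up, keep vital-status data open until 12 months after the last patient's first dose.
4. At each time point report the numbers known dead, known alive and unknown. Where status is unknown, give the best case (known dead ÷ all treated) and the worst case (known dead plus unknown ÷ all treated). Do not present an incomplete count as complete.
5. If Kaplan-Meier is used for mortality, use it with active follow-up, and not where late deaths are learned passively while survivors are censored at the end of the window.

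The cost is one record check or call per patient at month 3 and month 12, and later closure of the vital-status data. Patients undergo no extra procedure. If follow-up has already closed, as the past tense of the Study endpoint section may suggest, item 4 can still be applied, at the price of wider reported bounds.

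### The tabled adverse-event outcome counts only events related to tofacitinib, conflicts with the definitions elsewhere in the plan, and can understate total adverse events

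*Combined protocol and SAP*

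**What the plan says.** The combined protocol and SAP describes adverse events in several places, in different terms.

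- **Secondary Outcome Measures (table).** The single adverse-event row reads "Adverse events related to the treatment with tofacitinib", with a three-month time frame.
- **Brief Summary and Detailed Description.** Adverse events are listed as a secondary outcome with no limit by cause. The Detailed Description names "mortality, length of hospitalization, ocular complications, infections, and adverse events", so infections and ocular complications stand beside adverse events as outcomes of their own. Neither has a row or a time frame in the table.
- **Study endpoint.** The endpoint is "the absence of serious or treatment-related adverse events within three weeks after the final tofacitinib dose". The section then closes with: "Patients without AEs during this window were considered to have completed the trial and met the safety endpoint".
- **Mortality row.** "Number of participants with mortality at 30 days, 3 months and 1 year", with no limit by cause.

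The design is single-group and open label, "meaning that there will not be a placebo or control group". The Official Title is "An Open-Label Pilot Study to Evaluate the Safety, Tolerability, and Efficacy of Tofacitinib", so safety and tolerability come before efficacy. The Statistical Analysis Plan section is one sentence on healing time and does not mention adverse events. No section says who judges relatedness or by what criteria.

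**The concern.** With no comparator, harm from the drug cannot be separated from harm from the disease at group level. A related-only outcome passes that question to a judgement made event by event, without masking and without a written rule, and then leaves out every event judged unrelated. The disease offers a ready alternative explanation: the Detailed Description gives mortality of 30-35% in TEN and 5-15% in SJS and transitional forms.

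At stake is whether a reader of the results can see the total burden of adverse events in a pilot study that names safety first. Because the sections disagree, two analysts working from this plan could also report different adverse-event rates from the same data, each with support in the text.

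**Working it through.** The plan states no adverse-event figure, so there is none to reproduce. The check is a comparison of the definitions, plus simple arithmetic on the time windows.

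**Step 1: definitions in use.**
1. Any adverse event (Brief Summary and Detailed Description; also the literal sense of the last sentence of Study endpoint).
2. Related events only (outcome table).
3. Serious events of any cause, or related events (first sentence of Study endpoint).

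Take a patient whose only event in the window is non-serious and judged unrelated. This patient has no event under the table row and meets the first sentence of Study endpoint. The patient is not, however, among those without AEs whom the closing sentence credits with meeting the safety endpoint. The plan does not say which rule governs.

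**Step 2: windows, counted from first dose.** Inputs: dosing lasts 2 weeks (Arms and Interventions); the Study endpoint window is 3 weeks after the final dose; the tabled time frame is 3 months, about 13 weeks; total observation is 1-2 months (Study endpoint).

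- End of the Study endpoint window: 2 + 3 = 5 weeks.
- Literal window for serious events of any cause: end of week 2 to end of week 5, which is 3 weeks.
- Part of the tabled time frame outside it: 13 - 3 = 10 weeks, made up of 2 weeks of dosing and 13 - 5 = 8 weeks afterwards.
- If the window is read generously, as running from first dose to three weeks after the last, the uncovered part is 13 - 5 = 8 weeks.
- Stated observation against the tabled time frame: 3 - 2 = 1 month to 3 - 1 = 2 months short.

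**Step 3: what each definition captures.**

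| Event | Table row, to 3 months | Study endpoint, first sentence (literal) | Another outcome with a time frame |
|---|---|---|---|
| Judged related | Counted | Counted in window | Not needed |
| Death judged unrelated | Not counted | Counted in window | Mortality, to 1 year |
| Serious, non-fatal, judged unrelated, weeks 0-2 | Not counted | Not counted | None |
| Same, end of week 2 to end of week 5 | Not counted | Counted | None |
| Same, after week 5 to about week 13 | Not counted | Not counted | None |
| Non-serious, judged unrelated, any time | Not counted | Not counted | None |
| Infection or ocular complication judged unrelated | Not counted | Only if serious and in window | Named in the narrative; no row or time frame |

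The closing sentence of Study endpoint, read alone, would bring in non-serious unrelated events during its window. It contradicts the definition in the same section, so it cannot be relied on to close the gap.

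**Step 4: direction and size.** Let A be all adverse events in a period and U those judged unrelated. The tabled count is R = A - U. Since U is zero or more, R can equal A or fall below it, but never exceed it. The documents give neither A nor U, and no sample size, so A - R cannot be computed.

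**The case against.** The strongest reply is that one table row is not the whole safety plan, and much of that reply stands. The narrative lists adverse events without a limit by cause. Deaths count whatever their cause, to 1 year. The first sentence of Study endpoint joins serious and treatment-related with an or, which brings in serious events of any cause during its window. Infections and ocular complications are named outcomes in their own right.

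Three stronger readings are therefore tempting but not supported.

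- **That infections vanish once they are attributed to the disease.** They leave the adverse-event row, but they remain a named secondary outcome. The protection is thin, because that outcome has no row, definition or time frame, but it exists.
- **That harm from the drug will be under-reported.** With no attribution rule, error can run either way, and complications of the disease could also be charged to the drug. What holds is narrower: as a measure of total adverse events, a related-only count can only match the total or fall short of it.
- **That complications of SJS/TEN look like drug toxicity.** No section says so. It is a clinical inference, supported only indirectly by the background mortality and by the outcomes chosen for follow-up.

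It is also inferred from the open-label design, and not stated, that unmasked investigators make the relatedness judgement.

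The reply does not remove the gap in step 3. Nor does it explain why the table is narrower than the narrative it is meant to specify.

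**Conclusion.** The point holds in limited form. The tabled adverse-event outcome is narrower than the study's own narrative and conflicts with the Study endpoint section on both definition and window. Followed as written, it leaves non-serious events judged unrelated outside any clearly defined outcome with a time frame. It does the same for serious non-fatal events judged unrelated in about 10 of the 13 weeks on the literal wording, or about 8 of 13 on the generous one.

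The 10 and 8 weeks measure the length of the gap, not the number of events missed, and a reader should not turn them into an under-count. The effect on the reported rate is unknown, and any percentage would be invented.

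The conclusion rests on three assumptions: that the row is applied as worded, that the or in Study endpoint is read as covering serious events of any cause, and that dosing lasts two weeks. This is a cheap improvement to the reporting of a pilot study. It does not show that the safety results are wrong.

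**What to change.** 1. Change the adverse-event row in Secondary Outcome Measures to all adverse events and all serious adverse events, regardless of cause, from first dose to the stated 3 months, in all patients who took at least one dose.
2. Show relatedness as a second column, and state who judges it and by what criteria.
3. Count infections regardless of relatedness. Give infections and ocular complications their own rows and time frames.
4. Reconcile the Detailed Description and Study endpoint wording with this definition. In particular, choose between the first and last sentences of Study endpoint, and reconcile the 1-2 months of observation with the 3-month time frame.
5. Add a sentence to the Statistical Analysis Plan giving the adverse-event summary: the number and percentage of dosed patients with at least one event, by category.

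The cost is wording, a longer table and a less favourable headline rate. The related-only count stays available in the second column, so nothing is lost. Collecting events to 3 months may need contact beyond the stated observation period, but the existing 3-month row already implies that, and the mortality outcome already needs each patient's status at 3 months.

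### Read literally, the safety endpoint starts its count at the final tofacitinib dose, so a non-fatal event that begins and resolves during dosing need not stop a patient being labelled as meeting it

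*Combined protocol and SAP*

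**What the plan says.** The Study endpoint section has three sentences.

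- The first defines the endpoint as "absence of serious or treatment-related adverse events within three weeks after the final tofacitinib dose".
- The second says that most patients were followed for 3–4 weeks after treatment, "with the total observation period spanning 1–2 months".
- The third gives the classification rule: "Patients without AEs during this window were considered to have completed the trial and met the safety endpoint".

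Under Arms and Interventions, tofacitinib is given "twice daily, for the first week; and maintained tofacitinib 5mg-10mg, daily, for the second week", so a full course is two weeks.

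Safety also appears elsewhere. The Secondary Outcome Measures table lists "Adverse events related to the treatment with tofacitinib" with a time frame of up to 3 months, and "Number of participants with mortality at 30 days, 3 months and 1 year". The Detailed Description lists "mortality, length of hospitalization, ocular complications, infections, and adverse events" among the secondary outcomes. The Statistical Analysis Plan is a single sentence on skin healing, for which "the Kaplan-Meier product-limit estimates method was performed". It gives no analysis of the safety endpoint.

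**The concern.** A safety endpoint would normally cover the time on drug. This one, in its defining sentence, opens only when the drug stops, and no other sentence says that a serious or drug-related event during dosing makes a patient fail. The third sentence, which actually assigns the label, does not clearly restate either the event or the window, so two people classifying the same patient could reach different answers.

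The label matters because the section presents this as the trial's endpoint and the official title names safety first. There is also no control group against which a favourable figure could be judged. At stake is a report in which a patient with an on-treatment reaction is listed both as an AE case and as having met the safety endpoint.

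**Working it through.** The plan states no safety rate, event count or sample size, so there is no figure to reproduce. The check is day arithmetic followed by a reading of the sentences against each other.

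**Inputs.** Dosing: 2 weeks = 14 days (Arms and Interventions). Endpoint window: 3 weeks = 21 days after the last dose (Study endpoint, first sentence). Monitoring: 3–4 weeks = 21–28 days after treatment (second sentence).

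**Share of days before the window opens** = dosing days / (dosing days + post-dose days)

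- Full course, three-week window: 14 / (14 + 21) = 14/35 = 40%.
- Full course, four weeks of monitoring taken as the window: 14 / (14 + 28) = 14/42 = 33%.
- Dosing stopped after 7 days (assumption), three-week window: 7 / (7 + 21) = 7/28 = 25%.

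**What the third sentence's window could mean.** Taking 30.4 days per month:

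- Post-treatment monitoring alone is 21/30.4 = 0.7 to 28/30.4 = 0.9 months.
- With dosing added it is 35/30.4 = 1.15 to 42/30.4 = 1.4 months.

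The stated total of 1–2 months therefore fits best if it includes dosing. The total observation period and the three-week window are different periods, and the third sentence does not say which it means.

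**Classifying example patients**

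| Patient | First sentence | Third sentence | AE outcome row (related, to 3 months) |
|---|---|---|---|
| Drug-related, non-fatal event begins and resolves in the first week; dosing continues; nothing afterwards | Meets | Meets if the window is the 3 or the 3–4 weeks; does not if it is the 1–2 month total including dosing | Counted |
| Serious, unrelated, non-fatal event with the same timing | Meets | As above | Not counted (related events only) |
| Serious or related event after which no further dose is taken | Does not meet: the event follows the last dose taken | Not among those counted | Counted if related |
| Death within three weeks of the last dose taken | Does not meet, if death is treated as a serious AE (not stated) | Not among those counted, on the same condition | Counted only if judged related; mortality is its own row |
| One mild, unrelated AE within the three weeks | Meets | Not among those counted if AEs means any AE; meets if it is shorthand for the first sentence | Not counted |

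The first two rows show the literal gap: events that come and go while dosing continues or resumes. The last row shows the uncertainty about the event definition. Separately, the third sentence links completing the trial to having no AE. The documents give no other completion rule, so a patient followed to the end who had an AE has no defined status.

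**The case against.** **The window may not exclude dosing.** The nearest antecedent of the third sentence's window is the 1–2 month total, which probably includes dosing. On that reading on-treatment events do count. This stands as a limit on certainty: the post-dose window is the plain meaning of the definition, not the only possible reading of the section. It does not remove the fault, because that reading conflicts with the first sentence and the text does not choose.

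**AEs may be shorthand.** The third sentence may simply abbreviate the event named in the first. That is fair, so a second definition is not proven. The wording still needs to be made the same.

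**The gap is narrow.** An event after which no further dose is taken already falls in the window, and so does a death within three weeks of the last dose if it is classed as a serious AE. This stands. What escapes is a non-fatal event that begins and resolves while dosing goes on.

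**On-treatment harm might seem to go unrecorded.** A reader might infer this, but the documents do not support it. Drug-related AEs to 3 months and mortality are listed outcomes, and the Detailed Description adds infections and adverse events in general.

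**The outcome table might seem to contradict the endpoint.** It does not. Two outcomes with different windows can classify one patient differently without either being wrong.

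**Nothing depends on this endpoint.** No test, rate or decision rule is attached to it, and it is absent from the outcome tables. This stands and keeps the consequence small.

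**Conclusion.** The concern holds in a limited form. The defining sentence, read literally, leaves the 14 dosing days outside the safety window. That is 40% of the 35 days from first dose to the window's end, assuming a full two-week course. A patient with a non-fatal serious or drug-related event that begins and resolves in those days can be labelled as meeting the endpoint. The classification sentence leaves the window and the event uncertain and makes completion depend on having no AE.

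The 40% is a share of calendar time. It would be wrong to infer that 40% of events are missed or that the safety result is inflated by a known amount: with no event rate, onset timing or sample size in the documents, the number of patients mislabelled cannot be computed. Nor is the healing analysis affected. The consequence is confined to the reported safety label, but the rule as written can give a misleading label and is easy to correct. It should be fixed.

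**What to change.** Define the safety endpoint as no serious AE and no treatment-related AE from first dose through three weeks after the last dose taken, in all patients who took at least one dose, with any death in that interval counted as not meeting it. Use that event definition and that window in both the defining and the classifying sentence. Define trial completion by follow-up reached. Report serious AEs by relatedness alongside the endpoint, and state that the 3-month AE row remains a separate outcome with a longer window, so the two can still differ for late events.

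**Cost.** Two sentences are reworded and recorded events are reclassified. The documents describe no AE-collection procedure, so whether onset dates during dosing exist for every event cannot be judged.

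**Downsides.** The share of patients meeting the endpoint may fall. Serious complications of SJS/TEN itself, which the Detailed Description calls life-threatening, will count, and a single-arm study cannot separate them from drug harm by comparison. The split by relatedness helps but rests on judgement.

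**Timing.** The section is written in the past tense and the study dates run to 2025-07-31. If data are already collected, the change should be labelled post hoc and the result under the plan's present wording shown beside it.
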